
**SA1:** Examine the effect of the *BSM* intervention on the primary outcome of BNP intensity and interference between the intervention and attention control group controlling for prior BF experience across all data points.

**H1:** The *BSM* group will report significantly lower BNP intensity and interference at 1, 2, and 3 weeks and significantly lower cumulative BNP score over time compared to the AC group.

**SA2:** Examine the effect of the *BSM* intervention on secondary outcomes of BF exclusivity, BF self-efficacy, and maternal well-being.

**H2A:** The *BSM* group will have a higher proportion of women with exclusive BF at 6, 9, 12, 18, and 24 weeks and higher BF self-efficacy at all-time points compared to the attention control group. **H2B:** The *BSM* group will have higher maternal well-being compared to the attention control group at each time point.

**SA3:** Explore (1) the influence of pain sensitivity (quantitative sensory testing, select buccal cell and/or blood samples for pain sensitivity SNPs and in a subsample, DNA methylation of select sensitivity SNPs (40 participants (5 zero and 15 highest pain phenotype per group) on BNP intensity and interference; and (2) BF outcomes in SA2, maternal and pain self-efficacy over time between groups.

**SA4:** Explore (1) the influence of pain sensitivity and lactation (blood samples for pain sensitivity and lactation SNPs [*OXTR* and *PRL*]) on perception of milk supply (BSES and HH lactation scale).

Aligned with the Maternal and Infant Care goals of Healthy People 2020, NINR strategic themes of symptom science and self-management, NICHD optimal infant and maternal health during the fourth trimester, and the CDC *HEAR HER* campaign, the proposed study will address a major barrier to BF initiation and exclusivity by testing the effectiveness of the *BSM* intervention to decrease BNP intensity and interference and increase BF self-efficacy and support maternal well-being. The *BSM* intervention is easily accessible and clinically sustainable allowing for large-scale translation in health care and public health settings.

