**Justification of Sample Size:**

The sample size objective for the study is to recruit  $N = 280$  women who will be randomly assigned to the *BSM* or attention control study groups at a 1:1 ratio (140 per group). This objective provides 80% power ( $\alpha = 0.05$ , two-sided) to detect a standardized mean difference (Cohen's  $d$ ) of 0.39 or more between the *BSM* and attention control groups. It also provides 80% power to detect an odds ratio of 2.5 or more in exclusive BF between the two groups, assuming that the exclusive BF rate of the control group will be 10% higher than the national population rate in 2017 at 6, 9, 12, 18, and 24 weeks. These calculations account for "loss to follow-up" as high as 25% at 24 weeks, despite the substantially lower attrition (6%) in our pilot study. Based on our pilot study, we approached 78 women to meet our sample size of 60, with a failed screening rate of 25%. Thus, we intend to approach 374 women, which is 25% higher than our proposed study sample to meet our sample size. We anticipate that approximately 70% of the study sample will be WAHS or HHC patients.

In the pilot study, RM-ANCOVAs (with the baseline value of a measure as the covariate) revealed standardized mean differences larger than  $d = 0.39$  for the "main effect" of the intervention on BNP intensity ( $d = 0.45$ ), pain severity ( $d = 0.60$ ), cumulative pain ( $d = 0.64$ ), and BF self-efficacy ( $d = 0.48$ ) across the 1-, 2-, and 6-week time points. For BNP interference, the value of  $d$  was 0.39 at week 1, but smaller at weeks 2 and 6. Furthermore, the odds of exclusive BF in the intervention group are 2.9 times higher than the control group at 6 weeks, which is also higher than the hypothesized OR = 2.5. Therefore, we are confident that the sample size goal will be sufficiently powered to detect intervention effects on key variables for SA1 and SA2. Finally, the sample size estimate does not reflect our plans to conduct analyses based on repeated measurement of outcome variables at the 1, 2, 3, 6, 9-, 12-, 18-, and 24-week time points (due to the dearth of information regarding 24-week outcomes). Generally, the inclusion of data for an outcome variable across additional time points marginally enhances statistical power, especially for testing "main" and "interaction" effects of intervention and time.

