**SA1.** Initially, mixed effects linear modeling will be applied to contrast mean levels of pain at the 1-, 2-, and 3-week time points. The analyses will be repeated for a series of pain outcome measures, including BNP intensity, BNP interference, and cumulative BNP. The models will include “main” effects for intervention and time, an interaction between intervention and time, a random effect for “subject”, and the baseline value of the dependent variable as a covariate. Modeling results will be used to test for a time-by-intervention interaction. If the interaction is non-significant, the model will be re-fitted without it and testing will focus on the main effect of intervention. Regression diagnostics will be applied to all models to identify non-normality in residuals and potentially biasing effects of outlying observations. While mixed effects linear models are resistant to the impact of limited amounts of missing data, we will also utilize multiple imputation methods, as described below, to evaluate the sensitivity of model estimates and testing results to missing observations. Following evaluation of intervention effects at the 1-, 2-, and 3-week time points, we will proceed to assess differences in acute and cumulative BNP intensity and interference at 6, 9, 12, 18 and 24 weeks. Additionally, we will investigate whether subject-level “trends” or “growth curves” in pain levels across all eight study time points differ between the intervention and control conditions. If necessary, demographic variables will be included in the regression models both to account for potential confounding effects that might arise via imperfect randomization and to reduce unexplained between-subject variation in outcome variables.

**SA2. H2A.** We will start by investigating the intervention's effect on proportion of exclusive BF after week 6. Initially, the Pearson Chi-square test will be performed to detect the difference between intervention and control groups at 6, 9, 12, 18, and 24 weeks, respectively. Furthermore, a generalized linear mixed model with a logistic link will be applied to analyze the “main effect” of intervention and time, and “interaction effect” of intervention by time. The procedure to fit and re-fit the model will be similar to the approach for pain measures in SA1. The measure for BF self-efficacy, yield scale scores

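### The pooled exclusive-breastfeeding effect for H2A comes from a logistic mixed model whose odds ratio is subject-specific, so it is neither a difference in proportions nor comparable with the 2.5 and 2.9 used in planning

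*Combined protocol and SAP*

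**What the plan says.** H2A, in the aims under Purpose/Introduction, predicts that the intervention group will have a "higher proportion of women with exclusive BF at 6, 9, 12, 18, and 24 weeks". That is a statement about group proportions at five visits.

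Under Data Analysis and Management, SA2 H2A starts on the same scale: "Initially, the Pearson Chi-square test will be performed to detect the difference between intervention and control groups at 6, 9, 12, 18, and 24 weeks". It then adds that "a generalized linear mixed model with a logistic link will be applied to analyze the" main effects of intervention and time and their interaction. The model is specified by reference: "The procedure to fit and re-fit the model will be similar to the approach for pain measures in SA1". The SA1 model has "a random effect for “subject”, and the baseline value of the dependent variable as a covariate". In SA1, if the interaction is not significant the model is refitted without it and the intervention main effect becomes the focus.

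The Justification of Sample Size says: "It also provides 80% power to detect an odds ratio of 2.5 or more in exclusive BF between the two groups". The control rate behind that figure is given only in relative terms, "assuming that the exclusive BF rate of the control group will be 10% higher than the national population rate in 2017", and is applied to the same five visits. The section then sets a pilot odds ratio of 2.9 at 6 weeks beside the 2.5. It also says that the sample size does not reflect the planned repeated-measures analyses. Both figures are therefore two-group, single-visit odds ratios.

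The plan names no marginal odds ratio, risk difference or standardised proportion to be derived from the mixed model. It does not say that the model's odds ratio is subject-specific.

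**The concern.** In the SA1 linear models, the treatment coefficient is the same whether or not one conditions on the subject effect. In a logistic model it is not. The conditional odds ratio lies further from 1 than the population odds ratio, and the gap grows with the random-intercept variance, that is, with how persistent feeding status is within a woman.

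The mixed model is the only H2A analysis that yields one effect over weeks 6 to 24 and an interaction test. If its odds ratio is reported without a label, readers will set it against 2.5 and 2.9, as the sample-size section already does with the pilot figure. Its size would then partly reflect persistence rather than benefit. Each woman is in one arm only, so no contrast between arms is ever observed at a fixed random effect. The conditional odds ratio rests on the assumed random-effect distribution.

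**Working it through.** **1. The plan's own figures.** Inputs from the Justification of Sample Size: 140 per arm, 25% loss (140 × 0.75 = 105 analysed), two-sided alpha 0.05, power 80%.

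- For d = 0.39: 2 × (1.960 + 0.842)² / 0.39² = 103.2, so 104 per arm. Then 104 / 0.75 = 138.7, so 139, against 140 stated. This reproduces.
- For OR 2.5 no control rate is printed, so a range is needed. At an assumed control rate of 0.40, the intervention odds are 2.5 × 0.667 = 1.667, giving a proportion of 0.625 and a difference of 0.225. With null SE √(2 × 0.5125 × 0.4875 / 105) = 0.0690 and alternative SE √((0.240 + 0.234) / 105) = 0.0672, power is Φ[(0.225 − 1.96 × 0.0690) / 0.0672] = Φ(1.34) = 0.91.
- Over other control rates, power is at least 80% from about 0.17 to 0.67 and falls to 77% at 0.70. The 80% is plausible for a two-group comparison at one visit, but cannot be reproduced exactly.

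**2. From population to conditional odds ratio.** In a random-intercept logistic model with SD σ, an arm's proportion is the average of expit(α + σz) over standard normal z. Solve for α in each arm so that the two proportions have the required marginal odds ratio. The difference between the two α is the conditional log odds ratio. A close approximation is

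conditional OR ≈ exp[ln(marginal OR) × √(1 + 0.346σ²)].

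Example with σ = 3: √(1 + 0.346 × 9) = 2.03, and exp(0.916 × 2.03) = 6.4. Exact integration gives 6.8 to 7.3.

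Exact results for a marginal OR of 2.5, with assumed control rates of 0.30 to 0.60. Latent ICC is σ²/(σ² + π²/3).

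| Random-intercept SD | Latent ICC | Conditional OR | Ratio to 2.5 |
|---|---|---|---|
| 1 | 0.23 | 3.0 | 1.2 |
| 2 | 0.55 | 4.3 to 4.5 | 1.7 to 1.8 |
| 2.5 | 0.66 | 5.4 to 5.7 | 2.2 to 2.3 |
| 3 | 0.73 | 6.8 to 7.3 | 2.7 to 2.9 |
| 4 | 0.83 | 11 to 12 | 4.5 to 4.9 |
| 5 | 0.88 | 19 to 21 | 7.5 to 8.3 |
| 6 | 0.92 | 32 to 36 | 13 to 14 |

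For a marginal OR of 1.5, the conditional OR is about 1.8 at SD 1.5 and about 3.7 at SD 4.8. The ratios are 1.8 / 1.5 = 1.2 and 3.7 / 1.5 = 2.5.

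Read backwards at a control rate of 0.45, a reported conditional OR of 7 corresponds to a marginal OR of about 5.1, 2.5 or 1.8 at SD 1, 3 or 5.

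**3. Simulated visits at weeks 6, 9, 12, 18 and 24, true marginal OR 2.5.** All persistence settings are assumptions.

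- Status absorbing after stopping, with a share of visits redrawn independently; control rates 55, 52, 48, 42 and 36%. At adjacent-visit correlations of 0.44, 0.57 and 0.74, the fitted SD was about 2.1, 2.9 and 4.9, and the mixed-model OR about 4.4, 7.5 and 16 to 18. A logistic GEE on the same kind of data gave 2.3 to 2.5. At correlations of 0.82 or more the ratio exceeded 25 and the SD diverged.
- Latent autoregressive normal model. At 6-week correlations of 0.5, 0.7, 0.8 and 0.9, the mixed-model OR was 3.6, 4.9, 7.0 and 16.7. Standardising those same fits recovered about 2.5.
- True marginal OR of 1: the mixed-model OR was about 1.03, so the null value is shared.

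**The case against.** The strongest reply is that the plan already answers H2A on the right scale. The per-visit chi-square tests come first, compare proportions at exactly the five visits H2A names, and match the scale of 2.5 and 2.9. This stands, and it confines the point to the pooled and interaction estimates. It does not dispose of the point, because the tests are specified only to detect a difference. They come with no effect estimate and no overall effect across weeks.

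A subject-specific odds ratio is also a legitimate quantity, exclusive breastfeeding is a secondary outcome, and the plan never says that the model's odds ratio will be compared with 2.5 or 2.9. All true; the complaint is that the quantity is unlabelled and does not match H2A.

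Three stronger readings are tempting and not supported:

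- A reader might infer a fixed inflation, such as 2 to 7 times. By the approximation above, those factors for OR 2.5 need SDs of 2.45 and 5.03. The documents give no variance or correlation, and the ratio is about 1.2 at SD 1 and above 10 at SD 6.
- A reader might take exclusive breastfeeding as irreversible. Strong persistence is plausible, but the Significance section defines exclusivity as receiving only breast milk, with no rule that it cannot resume, and it is measured by repeated self-report.
- A reader might suspect a false-positive problem. The null value is the same on both scales, and no distortion of the test of no effect was found.

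**Conclusion.** The point holds for the mixed-model estimates in H2A. The plan's only pooled weeks 6 to 24 effect would be a subject-specific odds ratio, whose distance from the population value depends on a persistence parameter that the documents do not give. For a population OR of 2.5 it would be about 3.0 at SD 1, about 5 to 7 at SD 2.3 to 3, and about 17 to 20 at SD near 5. For an OR of 1.5 it would be about 1.8 to 3.7 over SD 1.5 to 4.8. These figures assume a normal random intercept and control rates chosen for illustration.

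The per-visit chi-square tests and the test of no effect are untouched. This is a fault of estimation and interpretation in a secondary outcome. It should be settled in the SAP before analysis.

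**What to change.** Keep the logistic mixed model and add SAP text that makes the reported H2A estimates population-averaged:

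- Integrate the fitted model over the random intercept to obtain each arm's proportion, the risk difference and the marginal odds ratio at weeks 6, 9, 12, 18 and 24, and averaged over those weeks.
- Give delta-method or bootstrap confidence intervals.
- Fit a logistic GEE as a check on the standardised results.
- Label any mixed-model odds ratio as subject-specific, report the random-intercept SD beside it, and do not compare it with 2.5 or 2.9.

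The cost is a few lines of text and one post-estimation step, with no new data. The reported odds ratio will look smaller than the one the mixed model prints.

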which range from 14-70. We will treat BF self-efficacy scores as "continuous" variable and follow the approach in SA1 to investigate the intervention effect on BF self-efficacy over time. **H2B.** Subsequently, we will assess intervention effects on maternal well-being - anxiety, depressive symptoms, fatigue, stress, and sleep disturbance over all the time points. Each of these variables' measurement scores will be treated as "continuous" and effects of the *BSM* intervention will be investigated following a similar approach as for the pain measures in SA1. Because these variables are highly interrelated, we will evaluate their response to intervention effects simultaneously. In this approach, differences in the quadrivariate means of these variables between the *BSM* and attention groups will be analyzed using multivariate mixed effects linear modeling in an approach analogous to that for the pain measures in SA1 but with the inclusion of covariances between random intercepts for the anxiety, depressive symptom, fatigue, and sleep disturbance scores at the subject level. Across the modeling procedures related to SA2, regression diagnostics will be applied to investigate suitability of distributional assumptions and potential biasing effects of outliers.

**SA3.** We will model effects of pain sensitivity SNPs on quantitative sensory testing measures, BNP intensity and interference, BF outcomes in SA2, and maternal and pain self-efficacy across all the time points. In addition, we will also assess the effects of individual quantitative sensory testing measures on all the outcome measures aforementioned over time. Analyses will utilize "linear/generalized linear" modeling with univariate and multivariate dependent variables, will account for correct temporal ordering among time varying measures, and will evaluate correlations between measures that jointly vary in time in response to other factors/covariates.

We have planned for attrition rates as high as 25%. However, our goal is to minimize attrition by instituting a participant outreach plan –namely, contacting participants to complete modules, providing monthly updates regarding child development, and encouraging women to remain involved. In statistical analyses, we will follow each model based only on "observed data" with sensitivity analyses in which Markov Chain Monte Carlo multiple imputation is used to assess the possibility and impact of "missing at random" data.

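### Once a non-significant interaction is dropped, the plan specifies no by-visit contrast for BF self-efficacy or maternal well-being, so the refitted main effect cannot test H2A (self-efficacy part) or H2B as worded

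*Combined protocol and SAP*

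**What the plan says.** In the specific aims (Purpose/Introduction), H2A predicts "higher BF self-efficacy at all-time points compared to the attention control group", and H2B predicts that the BSM "group will have higher maternal well-being compared to the attention control group at each time point". Follow-up assessments fall at weeks 1, 2, 3, 6, 9, 12, 18 and 24.

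Under Data Analysis and Management, the SA2 text sends BF self-efficacy to the SA1 approach and says that effects on the well-being scales "will be investigated following a similar approach as for the pain measures in SA1". The SA1 text sets the rule: "If the interaction is non-significant, the model will be re-fitted without it and testing will focus on the main effect of intervention".

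Two neighbouring outcomes get more. Exclusive BF has a separate chi-square test at each of weeks 6, 9, 12, 18 and 24. For pain, the model for weeks 1 to 3 is followed by an assessment of differences at weeks 6 to 24, and by a comparison of individual growth curves over all eight visits. The SA2 text does not say whether those two later pain steps also apply to self-efficacy and well-being.

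**The concern.** The hypotheses and the planned test address different quantities. The refitted model holds a single intervention effect, an average over visits, with no separate estimate for any week. A significant average shows that BSM is better overall. It does not show a benefit at each visit, and it is compatible with no benefit at some of them. A non-significant interaction does not close that gap, because failing to detect variation over time is not evidence that there is none.

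Constancy over time cannot be assumed in this trial. In Table 1 the BSM coaching texts run to week 6, while follow-up runs to week 24. The pilot lasted six weeks, and the sample size section concedes that little is known about 24-week outcomes. The same section reports that the pilot effect on pain interference was 0.39 at week 1 and smaller at weeks 2 and 6.

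At stake is what can be said about self-efficacy and well-being at individual weeks, above all late ones, when the interaction test comes out non-significant.

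**Working it through.** **The plan's own figure.** Justification of Sample Size: "This objective provides 80% power" to detect a d "of 0.39 or more between the *BSM* and attention control groups", two-sided alpha 0.05, 140 per arm, allowing 25% loss. Then 140 × 0.75 = 105 per arm. The standard error of a difference at one visit is √(2/105) = 0.138 SD, and 0.39/0.138 = 2.826. Power is Φ(2.826 − 1.960) = 0.807, so the stated 80% reproduces. It is power for one comparison.

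**Inputs for the rule.** From the documents: eight follow-up visits, 105 per arm after the worst-case loss, d = 0.39, two-sided 0.05. Assumed: one model over all eight visits, equal correlation ρ between visits, 105 per arm at every visit, no gain from baseline adjustment, and the effect profiles below. The documents give no ρ, so 0.3, 0.5 and 0.7 are shown.

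**Formulas.** Let d_t be the true effect at visit t and d̄ the mean over T = 8 visits.
- Interaction: chi-square on 7 df with noncentrality λ = (n/2) × Σ(d_t − d̄)² / (1 − ρ).
- Main effect: z = d̄ / SE, with SE = √[(2/n)(1 + 7ρ)/8].
- The two are independent under equal correlation, so the chance of a non-significant interaction together with a main effect significant for BSM is (1 − interaction power) × main-effect power.

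**Worked case:** d = 0.39 at weeks 1 to 18, zero at week 24, ρ = 0.5.
- d̄ = 0.39 × 7/8 = 0.341; Σ(d_t − d̄)² = 0.39² × 7/8 = 0.1331.
- λ = 52.5 × 0.1331/0.5 = 13.97; interaction power 78.7%, so it is missed in 21.3%.
- SE = √[(2/105)(4.5)/8] = 0.1035; z = 3.30; main-effect power 90.9%.
- Joint chance: 0.213 × 0.909 = 19%.

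**Joint chance by profile, 105 per arm:**

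| True effect | ρ = 0.3 | ρ = 0.5 | ρ = 0.7 |
|---|---|---|---|
| 0.39, zero at week 24 only | 38% | 19% | 3% |
| 0.30, zero at week 24 only | 54% | 35% | 13% |
| 0.39 fading to zero in equal steps per visit | 25% | 10.5% | 1.5% |
| 0.39 fading to zero linearly in calendar weeks | 31% | 14% | 2% |
| 0.39 to week 6, zero at weeks 9–24 | 2.5% | 0.2% | <0.1% |
| 0.30 to week 6, zero at weeks 9–24 | 9.5% | 2.7% | 0.1% |

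With 140 per arm, the first row becomes 24%, 9% and 0.6%, and the second 48%, 28% and 7%.

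**Comparison.** A contrast at one null visit, tested at two-sided 0.05, favours BSM in 2.5% of trials. If d = 0.39 holds at all eight visits, each visit has about 80% power, but all eight are significant in only 34%, 44% and 54% of trials (ρ = 0.3, 0.5, 0.7).

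**The case against.** A reader might infer that the plan treats a non-significant interaction as proof of a constant effect, and that a pooled result will be reported as a difference at week 24. The documents say neither. They say only that the model is refitted and the main effect tested; how the result would be worded is left open. The percentages above are therefore chances of reaching a branch on which a by-visit claim would be unsupported, not rates of false claims.

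The SA1 approach is also more than the refit rule. Its interaction test is written for weeks 1 to 3, and the later-week and growth-curve steps follow. If those carry over, much of the gap closes. With d = 0.39 fading linearly in calendar weeks, a 1-df test of intervention by linear time has power of about 89%, 97% and over 99% at ρ = 0.3, 0.5 and 0.7. It is weaker, at 42%, 54% and 76%, when d = 0.30 vanishes only at week 24. One eight-visit model is a fair reading of SA2 but is not written out.

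The larger figures come from a loss at week 24 alone, which is not what the end of coaching at week 6 would suggest. If the effect ends after week 6, the interaction test usually detects it and the chance is small. The pilot's shrinking effect concerned pain interference; for BF self-efficacy the plan reports d = 0.48 across weeks 1, 2 and 6. Using 105 per arm at every visit, without the baseline covariate, is pessimistic. These are secondary outcomes.

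All of this stands, and it limits the size of the risk. It does not supply the missing contrast: the hypotheses are worded by visit, and the only explicit test on the refit branch is of an average.

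**Conclusion.** The point holds as a mismatch between hypothesis and test. H2A (self-efficacy part) and H2B are claims about each visit. When the interaction is non-significant, the stated rule ends in one averaged effect, and no by-visit contrast is specified for these outcomes. That conclusion rests on the text alone and needs no simulation.

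Its practical size is uncertain and depends on the profile. It is substantial when a modest effect is absent at one late visit and the within-woman correlation is low, and negligible when an effect of the design size is absent from week 9 on. These figures depend on the assumed correlation, the assumed profiles and the single eight-visit model. The stronger reading, that the plan equates non-significance with constancy and will assert a week-24 benefit, is not supported. The sample size is unaffected, although it powers one comparison and not all eight visits jointly. The change should be made; it does not threaten the trial's primary aim.

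**What to change.** For BF self-efficacy and each H2B scale, write into SA2:
- The intervention-by-time term stays in the model whatever its p-value.
- The arm difference with 95% CI is reported at each of the eight visits from that model.
- The visit-averaged contrast from the same model is the overall test.
- Any statement about a given week rests only on that week's contrast.

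Alternatively, reword H2A (self-efficacy) and H2B to an average effect over visits; the main effect then tests what is claimed. In either case, state whether the later-week and growth-curve steps of SA1 apply to these outcomes.

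The cost is a few sentences and contrast statements, with no new data and no change in sample size. The downside is precision. Under the assumptions above, the 95% half-width at one visit is 1.96 × 0.138 = 0.27 SD, against 0.17, 0.20 and 0.23 SD for the average at ρ = 0.3, 0.5 and 0.7. Because significance at all eight visits is unlikely even under a constant effect of 0.39, the by-visit results are best presented as estimates with intervals.

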Prior to launch of the study, all research personnel will receive training on human subjects' research, HIPAA, and biological safety, handling and transportation. The study designated graduate assistants will develop a study binder of all protocols and each role will be established so that appropriate blinding procedures can be maintained throughout the study duration. [name] and the study Project Manager will train all research personnel (graduate assistants and peer counselors) on the standardized intervention, scripts, protocols for women who need referrals or follow-ups for BF support or maternal well-being, documentation of schedule data collection visits and establish weekly research team meetings. [name] and the Project Manager will conduct internal audits every three months to ensure fidelity in recruitment and procedures.

Table 1: Timeline of procedures

Week	Day	Measure	Location	Time	Compensation
Prenatal visit	Recruitment	Study flyer, Breastfeeding Basic Information	HH, WAHS, UCHC prenatal clinic	5 min	\$0
0	Recruitment	Initial Screen	Hospital/ Smart phone	5 mins	
0	Baseline Assessment	Consent 
 
Verification of CLC evaluation of breastfeeding
 
Buccal cell swabs and/or blood collection (15 ml or 3 teaspoons)
 
QST
 
Questionnaires
 
Demographics
 
Breastfeeding Specific Factors: Maternal and Infant Breastfeeding History
 
	Hospital	1 hr Links will be shared for individuals to	\$25 UConn Greenphire Gift Card or ecard

		
 
• Breastfeeding Log (BL) 
 
◦ MAIBB-R
 
◦ Algorithm
 
 
 
• Breastfeeding Battery (BB) 
 
◦ BSES-SF
 
◦ Ongoing Breastfeeding Assessment
 
 
 
• Pain Interpretation Scales (PIS) 
 
◦ Coping Strategies Questionnaire
 
◦ McGill Pain Questionnaire
 
◦ Brief Pain Inventory
 
◦ Visual analogue scale
 
 
 
• Maternal Well-Being (MWB) 
 
◦ NINR CDEs (Anxiety, Sleep, Fatigue, Perceived Stress Scale, Index of Self-Regulation, Self-Efficacy for Managing Chronic Illnesses Scale, Global Health)
 
◦ EPDS
 
◦ Karitane Parenting Confidence Scale
 
 
 
		complete on their own	

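### The H2B joint model names only random-intercept covariances between the well-being scores; without a within-visit residual covariance, its joint time-by-intervention test rejects too often when same-visit errors are correlated.

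*Combined protocol and SAP*

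**What the plan says.** H2B (Purpose/Introduction, specific aims) predicts that the intervention group "will have higher maternal well-being compared to the attention control group at each time point". The analysis is in Data Analysis and Management, SA2.

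- **Why joint:** "Because these variables are highly interrelated, we will evaluate their response to intervention effects simultaneously".
- **What is compared:** "differences in the quadrivariate means of these variables", by a multivariate mixed model built like the SA1 pain model.
- **What is added to SA1:** the model is fitted "with the inclusion of covariances between random intercepts for the anxiety, depressive symptom, fatigue, and sleep disturbance scores at the subject level". Nothing is said about the residuals, either within one score or between scores.
- **Order of testing, from SA1:** "Modeling results will be used to test for a time-by-intervention interaction", and then "If the interaction is non-significant, the model will be re-fitted without it and testing will focus on the main effect of intervention".
- **How the scores are collected:** Table 1 (Design, Procedures, Materials and Methods) places them in one maternal well-being block, "NINR CDEs (Anxiety, Sleep, Fatigue, Perceived Stress Scale, Index of Self-Regulation" and further scales, with the depression scale in the same block. The block is scheduled on a single day at each follow-up point.

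The SA2 text lists five well-being variables. The joint model has four; stress is missing from it.

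**The concern.** A random intercept describes a woman's stable level on a score. Covariances between intercepts say that women who are generally more anxious are also generally more tired. They do not describe a bad week that moves anxiety, mood, fatigue and sleep together on one questionnaire. That dependence belongs in the residual covariance between scores at the same visit, which the plan does not mention.

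The omission matters most for the test that comes first. Time-by-intervention contrasts compare visits within a woman, so the intercepts drop out and the dependence between outcomes comes only from the residuals. A model with residuals independent across scores counts partly repeated evidence as separate evidence. The joint interaction would then be declared significant too often. That decides whether the interaction stays in the model and whether H2B is reported as an effect that varies over time.

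**Working it through.** **Plan's own figure.** The documents give no power or error rate for the H2B joint tests. The nearest figure, 80% power for d = 0.39, reproduces: 140 × 0.75 = 105 per arm; 0.39 × √(105/2) = 2.83; Φ(2.83 − 1.96) ≈ 0.807. It does not bear on this point.

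**Inputs from the documents.** Four outcomes in the joint model; eight post-baseline visits; α = 0.05; 140 per arm with up to 25% loss.

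**Assumed inputs.** Same-visit residual correlation ρ, common to all pairs, from 0 to 0.7. Where needed, a random intercept carrying half of each score's variance (0.3 and 0.7 also tried) and a correlation of 0.6 between intercepts. The random intercept is taken to be adequate over time within each score.

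**1. Model.** For outcome q at visit t: y = mean + b_q + e_qt, with Cov(b) = G left free and Cov(e) = R between outcomes at one visit. The literal fit takes R as diagonal.

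**2. Joint interaction test, balanced data.** With diagonal R the statistic is the sum of four 7-df chi-squares treated as independent. It is referred to chi-square on 4 × 7 = 28 df (critical value 41.34). Its true null law is Σ λ_j χ²₇, where the λ_j are the eigenvalues of the residual correlation matrix: 1 + 3ρ once and 1 − ρ three times. The mean stays at 28, but the variance is 14 × Σλ_j² = 56(1 + 3ρ²). At ρ = 0.5 the eigenvalues are 2.5, 0.5, 0.5, 0.5, and the variance is 98 instead of 56.

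| ρ | 0 | 0.2 | 0.3 | 0.5 | 0.6 |
|---|---|---|---|---|---|
| Rejection at nominal 5% | 5.0% | about 6% | 7.0% | 9.8% | 11.3% |

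With five outcomes (stress included) the rates at 0.3, 0.5 and 0.6 are about 7.7%, 11.1% and 12.9%.

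**3. Checks on step 2.**
- With 25% monotone dropout, using the limiting maximum-likelihood values: 6.0%, 7.1% and 9.9% at ρ = 0.2, 0.3 and 0.5.
- With three visits (8 df) and the same dropout: 5.9% to 11.6% for ρ from 0.2 to 0.7.
- Simulation with 105 per arm, eight visits, complete data and 4,000 replicates (standard error about 0.3 percentage points):

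| ρ | 0 | 0.3 | 0.5 |
|---|---|---|---|
| Diagonal residuals | 5.5% | 6.8% | 10.1% |
| Free cross-outcome residual covariance | 5.5% | 5.0% | 5.6% |

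**4. Joint main effect after refitting.** This test uses each woman's average over visits, whose true covariance is G + R/T (T = number of visits). When R is forced to be diagonal, the free intercept covariance absorbs the missing part: its off-diagonal becomes G + R/T. The variance of the average is therefore right. The calculated level is 5.0% at every ρ, with 0% or 25% dropout; the simulation gave 5.3% to 6.0% with no trend in ρ. Single-outcome main-effect tests also stay at 5.0%.

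**5. Joint test at one visit, if run.** The true off-diagonal covariance is G + R; the fitted one is G + R/8. With the intercept carrying half the variance and ρ = 0.5, that is 0.30 + 0.25 = 0.55 against 0.30 + 0.25/8 = 0.33. Relative to the fitted covariance, the true one has eigenvalues (1 + 3 × 0.55)/(1 + 3 × 0.33) = 1.33 once and 0.45/0.67 = 0.67 three times. The statistic's mean is about 3.35, where the test expects 4. The week 1 rates, with 25% dropout, are 3.9%, 3.5% and 2.8% at ρ = 0.2, 0.3 and 0.5. Over the range tried, about 2.5% to 4%.

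**The case against.** The strongest answer is that the plan is silent, not wrong. It does not say that residuals are independent across scores, nor that the intercept covariances are the only link. A statistician fitting the model could add a residual covariance without departing from the text. This stands: a reader might infer that the plan sets the same-visit correlation to zero, and the documents do not say so. Silence does not settle the matter, however. The plan names one addition to SA1, and a fit that adds only that has a miscalibrated first test.

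A reader might also infer that all the joint tests are faulty. Step 4 shows otherwise. The main-effect test that follows a non-significant interaction is sound, and so are the main-effect tests for each score alone, which SA2 also plans.

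Nor do the documents prescribe a joint test at each visit. H2B speaks of "higher maternal well-being compared to the attention control group at each time point", but that can be examined score by score, so the conservative figures apply only if such a joint test is run. That the interaction comes first in the joint model is a fair reading of its being built like SA1, though it is not spelled out there.

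The size rests on an assumed ρ. The strong relation between the scores could lie mostly in stable differences between women, which the intercepts do capture. At ρ = 0 there is no error, and at 0.2 it is one percentage point.

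Finally, because H2B is directional, a reader might want the joint test replaced by an averaged score. That choice depends on whether the effects are similar across scales, which the documents do not establish. It is separate from the covariance question and is not part of this point.

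**Conclusion.** The point holds as a conditional one. If the H2B model is fitted with only the dependence it names, and same-visit errors are correlated, the joint time-by-intervention test is too liberal: about 7% to 10% in place of 5% at correlations of 0.3 to 0.5, and 11.3% at 0.6. Some positive correlation is likely, since the scales are answered in one sitting and the plan itself treats them as strongly related, but its size is unknown. The result barely changes with 25% dropout or with the share of variance carried by the intercept.

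H2B is a secondary hypothesis. The primary pain analysis and the sample size of 280 are not affected. The correction is worth making because the affected test steers the rest of the sequence and the change is small.

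**What to change.** In Data Analysis and Management, SA2/H2B, state that the multivariate model will have an unstructured residual covariance between outcomes within each visit, in addition to the covariances between subject-level random intercepts. Say explicitly that the SA1 order of tests applies to the joint model.

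Settle at the same time whether the joint model has four outcomes or five, since stress is listed but not included. The extra covariance parameters number 4 × 3/2 = 6 for four outcomes, or 5 × 4/2 = 10 for five.

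The cost is a sentence or two of SAP text and a somewhat heavier model, with no new data. Convergence may need checking, so a fallback should be named in advance, for example robust standard errors clustered on the woman for the joint tests.
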